Recruitment. Participants will be recruited from a variety of potential sources, including psychiatric centers, pediatric offices, schools, parent support groups, and through advertisements placed in community locations and in local media outlets, and through direct mailings. Our center has an extensive history of running large scale ADHD clinical trials. Between 2002 and 2008, our center recruited 600 families with ADHD children for 6 clinical trials, and recruitment targets for all studies were met. Currently, our Center has a waitlist of over 300 adolescents between the ages of 12-16 whose parents are interested in participating in treatment studies for ADHD In addition, in the past year, our Center has provided medication or psychosocial treatment to approximately 150 adolescents with ADHD. Among these adolescents, the majority, (53.8%) were not actively taking ADHD medication upon referral to our clinic. During the past year, our Center also enrolled children and adolescents with ADHD for one foundation funded, one industry funded, and four federally funded clinical trials (two focused exclusively on adolescents), with all projects meeting or exceeding annual recruitment goals. Hence, we expect to meet the projected recruitment goals in a timely fashion. Families who previously have expressed interest in receiving information about studies, will be contacted via mail, email, and/or phone depending on the contact information they have provided. Information distributed to families will invite the parents to call the FIU Center for Children and Families (CCF) to receive additional information or to register to participate in the project.

Inclusion/Exclusion. Participants will be screened over the phone to ensure that only eligible participants are brought in for intake. Inclusion criteria will include a DSM-5 diagnosis of ADHD, a Full Scale IQ above 80, and elevated risk for the development of substance use problems as outlined above. ADHD diagnoses will be established based on information gathered from parent, teacher, and adolescent self-report as well as records of previous evaluations and school history provided by parents. The Full Scale IQ criterion will be considered met if upper bound of the 95% confidence interval for any composite score on the WASI is equal to or greater than 80. Following recommendations by Sibley et al. (2012), adolescents with fewer than 6

Table 4. NHSDAH Age-based norms forfrequency of alcohol use (days per month)							

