Concerta was chosen as the stimulant medication to remain consistent with Riggs and colleagues' (2011) major medication trial in adolescents with combined ADHD and established substance use disorder. Optimal dose will be defined as one enabling adolescents to reach a level of home/school functioning considered good with no further room for improvement that represents a meaningful change from baseline with a tolerable level of side effects. A similar definition has been employed in the MTA and other large ADHD trials (Vitiello et al., 2001, Palumbo et al., 2008, Collins et al., 2006). All adolescents in this arm will start the protocol taking medication seven days a week (no drug holidays). Adolescents who have not previously taken stimulant medication for ADHD will be started on the lowest available dose of Concerta (18mg which approximates 5mg TID of MPH). Adolescents who are already taking medication for ADHD at the time of randomization will have a consultation with the study doctor to determine whether their current medication can be safely continued with the study medication or whether changes are needed (e.g., safely withdrawing the other medications, reducing dose, etc.) prior to initiating the study medication. After one week, parents and teens will rate efficacy and tolerability using parent symptom rating scales, the parent and teen versions of the Impairment Rating Scale (IRS) and the Clinical Global Impression Scales for ADHD (CGI; Rapoport et al., 1985). The Pittsburgh Side Effects Rating Scale (PSERS) will be used to assess drug tolerability. At each medication assessment visit, a study physician will meet with the family to review the efficacy and tolerability ratings and complete the ADHD CGI-I/S (Improvement and Severity Scales) to determine the need for a dose change. The assessing clinician will be instructed to increase the dose (to 36mg, 54mg, then 72mg, respectively) unless the physician believes the subject's functioning has been optimized (CGI-S <3) or the teen cannot tolerate a higher dose. This threshold has been found to be a valid definition of optimal dose (Gao et al., 2006). This process will be repeated in one-week intervals until the lowest effective dose that is well-tolerated has been identified. We chose a one week duration for each dose to allow for a thorough assessment of the therapeutic effects of that dose and timely collection of ratings from home. These one-week follow-up appointments may take place in

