Aim 3: The third aim is to determine if, given nonresponse to the BEI, it is preferable to augment treatment with enhanced psychosocial intervention or multimodal treatment. As previously stated, we expect less than 50% of the sample to respond to the BEI, leaving at least 150 treatment-resistant adolescents to be randomized into one of the three treatment arms: (1) No treatment, (2) PT/ACBT, (3) PT/ACBT + MED. Using the general linear modeling techniques as implemented by SAS PROC GLM, we will examine differences between the treatment arms over post-treatment and one year follow-up measurement points with fixed effects of treatment arm. Analyzing each time period will address separate questions about the effect of intervention immediately post-treatment and at one-year follow-up. For these analyses, mixed linear models and/or GEE strategies will be used (Hedeker et al., 2006). Primary and secondary outcome measures will be evaluated separately (see Table 5). As our sample size permits, as a secondary analysis, we will also examine whether changes in the secondary outcomes listed above following treatment mediate response to treatment and substance use during the follow up phase.

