Power Analysis: For Aim 1, previous evaluations of BEI report a large effect of treatment on days of alcohol use (d=2.67; Winters et al., 2007). A sample size of 300 (G*Power 3.1.2 software), with alpha of 0.05 for a two-tailed test, will provide power = 0.96 to detect a small treatment effect size of 0.25 if there are no drop outs. Assuming a maximum dropout rate of 15%, as shown in previous studies with Hispanic adolescents with behavior problems (Pantin et al., 2009; Prado et al., 2007), the power drops slightly to 0.90. We also plan to measure the impact of concurrent medication use on treatment effect. For this analysis there are now two groups of participants, those currently using stimulant medication and those not using stimulant medication. The sample size of 300 with a maximum drop-out rate of 15% will provide .90 power to detect an interaction effect of medication, assuming a small pre-test to post-test correlation among measures (r = .25). For Aim 3, a sample size of 150 with a maximum drop-out rate of 15% will provide .90 power for a treatment effect size of .40, which is adequate considering that most ES for similar treatments range between .40 and .80 (Waldron & Turner, 2008). Thus, the sample should be sufficient to detect significant effects of treatment as well possible prediction models.

c. Potential Risks

Risk: Participants may experience mild and transitory psychological discomfort from completing research measures that deal with emotionally laden material, including reporting on illicit drug use and other antisocial or illegal behaviors, which may be uncomfortable for some participants. **Procedure:** We will inform participants of the NIH Confidentiality Certificate prior to collecting any data for the study, which will shield the research data from a subpoena or court order. In addition, participants and their parents will be advised to ask questions of study personnel if confidentiality is of a concern, and to refrain from answering questions that cause them personal distress.

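### Aim 3 does not account for ADHD medication already in use at randomisation, so the PT/ACBT+MED versus PT/ACBT contrast may be diluted by an unknown amount

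*Combined protocol and SAP*

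**What the plan says.** - **The contrast.** Under Research Design and Methods, PT/ACBT+MED is PT/ACBT with a concurrent stimulant added and nothing else changed. The Aim 3 hypothesis expects the largest effects in that arm.
- **Background medication.** The Interventions section, describing the medication arm, provides for "Adolescents who are already taking medication for ADHD at the time of randomization" and sends them to the study doctor. The Inclusion/Exclusion text does not bar current users. No section says what happens to ADHD medication in the PT/ACBT or monitoring arms.
- **How common it may be.** Recruitment reports that, of about 150 adolescents treated at the centre in the past year, 53.8% "were not actively taking ADHD medication upon referral to our clinic".
- **Aim 3 randomisation and model.** The plan expects non-response, "leaving at least 150 treatment-resistant adolescents to be randomized into one of the three treatment arms". No allocation ratio or stratification factor is given. Arms are compared "with fixed effects of treatment arm", and no medication term is named.
- **Aim 3 power.** The Power Analysis says that "a sample size of 150 with a maximum drop-out rate of 15% will provide .90 power for a treatment effect size of .40".
- **What is planned on medication.** The same section plans to compare current stimulant users with non-users and to test an interaction. That analysis is sized on 300, which is the brief-intervention sample, and does not reappear under Aim 3.

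**The concern.** The comparison of PT/ACBT+MED with PT/ACBT is the trial's test of adding medication. If some PT/ACBT teens already take a stimulant, and some PT/ACBT+MED teens were taking one before the study supplied it, the average difference between the arms mixes teens who start a stimulant with teens for whom less changes. The observed difference would then understate the effect of starting medication. A null result would be hard to interpret, because the plan offers no Aim 3 analysis that separates the two groups. The sponsor has already recognised the variable for the brief intervention, but it is missing from the aim in which medication is itself part of the randomised treatment.

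**Working it through.** **Inputs**
- 150 randomised, 15% dropout, three arms: Power Analysis and Aim 3. Equal allocation is assumed, giving 150 × .85 = 127.5 evaluable and 127.5 / 3 = 42.5 per arm.
- Two-sided alpha of .05: stated for Aim 1 ("with alpha of 0.05 for a two-tailed test") and assumed to carry over.
- Effect sizes of .40 to .80: the range the Power Analysis cites for similar treatments. The metric is not stated.
- Share p already medicated: unknown. The proxy is at most 100 − 53.8 = 46.2%; 20% is an assumed lower value.
- Share g of the benefit that existing users still gain in the medication arm: unknown; 0 and .5 are assumed.

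**The plan's own figure**

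The test behind .90 is not stated. One reading comes close: a three-arm group-by-time test with .40 read as d (f = d/2 = .20), two time points and r = .25, which the plan gives only for the Aim 1 medication analysis.

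λ = f² × N × m / (1 − r) = .04 × 127.5 × 2 / .75 = 13.6, power **.914**.

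A one-time three-arm ANOVA gives .985 at f = .40 and .502 at f = .20, so neither matches. The .914 calculation has no term for background medication.

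**Dilution of the pairwise contrast**

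Diluted effect = d × k, with k = 1 − p × (1 − g). The within-arm SD is held fixed. Power is from the noncentral t with 42.5 per arm and noncentrality d × k × √(42.5/2).

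| Scenario | k | d = .8 becomes | Power | d = .4 becomes | Power |
|---|---|---|---|---|---|
| No background use | 1 | .80 | .95 | .40 | .45 |
| p = 20%, g = 0 | .80 | .64 | .83 | .32 | .31 |
| p = 46.2%, g = .5 | .769 | .615 | .80 | .308 | .29 |
| p = 46.2%, g = 0 | .538 | .43 | .50 | .215 | .17 |

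In the repeated-measures model that came close to .90, applied to two arms (N = 85, f = .20 × k), power is .845 with no background use. It falls to .66, .63 and .36 in the same three scenarios.

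**What stratifying or adjusting does**

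In a simulation with p = .462, g = 0 and a true effect of .80, the average contrast was:
- .433 unadjusted;
- .433 with baseline use as a covariate;
- .437 stratified and adjusted;
- .80 among non-users, from a model with an arm-by-use term.

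The expected diluted value is .538 × .80 = .430. Stratification and a main-effect covariate therefore leave the dilution in place.

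Without stratification, at 50 per arm and 46.2% use, the chance that two arms differ in baseline use by 10 points or more is about 37%, and by 20 points or more about 6%.

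**Non-user estimate**

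At 46.2% use it rests on 42.5 × .538 = 22.9 evaluable per arm. Power by the same t-test is .26 at d = .4 and .75 at d = .8.

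**The case against.** - **Cause.** A reader might infer that the dilution happens because Aim 3 does not stratify or adjust. It does not. Dilution would come from background use in the comparison arm, and the simulation shows the average contrast unchanged by either step. This objection stands.
- **Imbalance.** A reader might also infer that chance imbalance in prior use biases the comparison. After randomisation, such imbalance is random error that the test's alpha already covers. It costs precision only.
- **The 46.2%.** It is tempting to treat this as the trial's rate. It describes clinic patients at referral, on any ADHD medication. They are not brief-intervention non-responders, who are randomised at an assessment 6 to 18 months after treatment. The true share could be well below or above it.
- **No added gain for users is a worst case.** The medication arm includes repeated dose review and regular follow-up, from which an existing user could benefit. The documents also do not say what PT/ACBT teens take after randomisation, so similar exposure in the two arms cannot be assumed.
- **Model.** Aim 3 plans repeated-measures methods, and a one-time t-test gives lower absolute power. This stands for the level. The loss from dilution appears in both models.
- **Estimand.** What study-managed medication adds in a mixed population is a legitimate question, and the documents do not confine Aim 3 to new starters. This stands, and it argues against making the non-user contrast the main test.

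**Conclusion.** The gap is real. Teens already on ADHD medication can enter Aim 3, the arms being compared are meant to differ only by a stimulant, and the Aim 3 model has no term for background use. The all-randomised PT/ACBT+MED versus PT/ACBT contrast may therefore be diluted.

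The size cannot be fixed from the documents. Over the scenarios shown, power falls from .95 to between .83 and .50 at d = .8, and from .45 to between .31 and .17 at d = .4. These figures rest on equal allocation, 15% dropout, two-sided .05, a single-time t-test, and assumed values for both the share medicated and the gain users keep.

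Two stronger conclusions might be drawn and are not supported. One is that the plan overlooks medication altogether; it plans a user/non-user interaction, but only for the brief intervention. The other is that a null Aim 3 result would be worthless; it would still answer the mixed-population question. The monitoring versus PT/ACBT contrast is not diluted in this way, and monitoring versus PT/ACBT+MED is affected only in its medication component.

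The change should be made because it is cheap and bears directly on how the medication result is read.

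**What to change.** 1. Carry the current-stimulant-use variable from the Power Analysis into Aim 3: stratify the second-stage randomisation on it and include it as a covariate. State that this is for balance and precision, not to remove dilution.
2. Pre-specify, as a secondary analysis, an arm-by-baseline-use term and the PT/ACBT+MED versus PT/ACBT estimate among teens not on a stimulant at randomisation. Report it beside the all-randomised contrast, which stays the main test.
3. Confirm that the Treatment History Form, listed in Table 5, captures current stimulant use at randomisation; the protocol does not describe its content.

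**Cost.** One stratification factor, a few sentences of analysis plan, and possibly one form item. If second-stage randomisation has already begun, stratification can cover only later entrants, but the covariate and interaction can still be written in before analysis. The main drawback is precision: about 23 evaluable per arm at 46.2% use, with power of about .26 at d = .4 and .75 at d = .8. The non-user estimate should therefore guide interpretation and not serve as a confirmatory test.

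This concerns recording, randomisation and analysis only. No view is given on how any participant's medication should be managed.

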The goal of this study is to evaluate the efficacy of a Brief Early Intervention (BEI) for reducing early alcohol and marijuana use in a group of adolescents (age 12-16) with ADHD who are at elevated risk for substance use problems. All adolescents will receive the BEI (based upon Teen Intervene). The Brief Early Intervention (BEI; 5 individual sessions with adolescent with some parent involvement during 3 of these sessions) will consist of a modification of a brief early intervention program designed by Winters (Winters & Leitten, 2007) with the addition of enhanced decision making skills. Due to the existing support for the intervention, the criterion for eligibility (elevated risk factors for early initiation of substance use), and concern for randomizing families with adolescents at risk for worsening substance use outcomes into a control (no treatment) condition for one to two years, no control condition is used in the current design at the first level of intervention. Similarly, due to the time required to see a potential effect of the treatment (6 months post-brief intervention), a wait-list control condition was not considered.

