Adolescents will be evaluated for treatment non-response to the BEI at 6, 9, 12, 15, and 18 months posttreatment. Non-response is defined as non-normative use of alcohol, marijuana, or other drugs in the past 90 days. Alcohol and marijuana are the outcomes of interest in this study; however, non-normative use of any psychoactive substance will be considered non-response. Alcohol use norms by age are presented in Table 4 and any marijuana use in adolescence is considered non-normative (NHSDAH, 2007). Tobacco and caffeine products are excluded from consideration. For alcohol, marijuana, and other drugs, frequency and quantity of substance use will be collected for the past 90-days using the Substance Use Questionnaire (SUQ). Adolescents who do not demonstrate a response to the BEI at the 6, 9, 12, 15, or 18 month assessment (i.e., use substances at non-normative levels) will be randomized to either (1) No Additional Treatment Monitoring Group, (2) Parent Training/Adolescent CBT (PT/ACBT; e.g., 12 weeks of parent training and adolescent CBT) (3) PT/ACBT plus concurrent stimulant medication (PT/ACBT+MED). Adolescents who demonstrate immediate initial response will be released from treatment and assigned to a monitoring condition in which they are reassessed at 9, 12, 15, and 18 months. Any adolescent who demonstrates non-normative use at any of the follow-up assessments as defined above will be immediately eligible for randomization to further treatment (as detailed above). Adolescents and parents will complete an assessment battery at the randomization point as outlined in Table 5 unless randomization occurs immediately following the 6 or 12 month assessment (in which case the measures will not need to be repeated).

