The Parent Training and Adolescent CBT (PT/ACBT) will be longer in duration than the BEI (12-family sessions with individual adolescent, parent, and joint adolescent and parent time), and will include additional parent training in behavioral modification, adolescent and parent contracting, and adolescent decision making skills. The PT/ACBT and Medication (PT/ACBT+MED) condition will be identical to the PT/ACBT condition but will include concurrent stimulant medication administration. Recruitment will continue on a rolling basis over the course of the year. The primary outcome measure will be alcohol and marijuana use. Secondary outcome measures include adolescent ADHD symptom severity, situational impairment (e.g., academic and social impairments, parental monitoring), proximal deviancy measures (e.g., delinquency, deviant peer affiliations, risky sexual behavior, family conflict), and teen attitudes and beliefs (motivation to use, self-efficacy). (see Table 5).

Participants. Three-hundred adolescents with ADHD between the ages of 12-16 who displayed elevated risk for substance use problems (but not severe abuse of alcohol, marijuana, or other drugs) will be recruited beginning in YR01 of the project on a rolling basis. Elevated risk is defined as the presence of at least risk factor from each of the following two categories of risk:

- 1. General Risk Factors
 - a. Elevated symptoms of ODD or CD (Elevated parent or teacher scores on relevant subscales of the CBCL, TRF, or the DBD-RS).
 - b. Elevated conflict with parents (Elevated parent-reported conflict on the CBQ)
 - c. Low parental monitoring (Parents are aware of teen activities or teens disclose activities to parents only some of the time or less often.)
 - d. Academic failure (Teens have previously failed a grade in school or earned Ds or Fs on most recent report card.)
- 2. Substance Use Specific Risk Factors
 - a. Adolescent non-normative use of alcohol or other drugs indicated either by a positive urine drug screen or by adolescent self-report on the Substance Use Questionnaire.
 - Adolescent use of cigarettes or e-cigarettes indicated by self-report on the SUQ or the E-Cigarette Questionnaire.
 - c. Elevated parental use of alcohol or other drugs indicated by AUDIT score of 8 or higher or parent self-report of any use of other drugs for non-medical reasons.

Revised Protocol Version 06042019

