- d. Family history of substance use problems indicated by adolescent report of parent substance use problems or parent report on the Mann Family Tree indicates at least one parent or other family member is either a possible problem drinker/user or a definite problem drinker/user.
- e. Other child in home using drugs or alcohol indicated by parent or adolescent report that at least one other child in the home uses alcohol or other drugs on the Mann Family Tree.
- f. Perceived peer substance use indicated by adolescent report that at least one peer uses alcohol or other drugs.

Attempts will be made to recruit at a rate of approximately 100 participants per year during YR01 through YR03. All participants will receive the brief early intervention. The participants will be approximately 20% female and 80% male as these gender rates are representative of epidemiological prevalence estimates of ADHD (American Psychiatric Association, 2000). The combined population of Broward and Miami Dade Counties is approximately 57% Hispanic, 25% Caucasian, and 18% African American. We expect to reach a goal of at least 75% minority enrollees (see targeted enrollment chart), surpassing the percentage in the MTA (MTA, 1999). The diversity of our sample will allow us to examine the moderating effects of race/ethnicity on the impact of the proposed adherence intervention.

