Aim 1: We will investigate response to a brief early intervention (BEI) for substance use among adolescents with ADHD. We hypothesize that approximately 50% of adolescents will show meaningful response to the BEI, as evidenced by no more than normative substance use assessed at 6-months following treatment. Aim 2: We will also test whether key variables associated with ADHD (ADHD symptoms) and with the development of substance use (parental monitoring, social impairment, academic functioning, family conflict, deviant peer affiliation and peer drug use, risky sexual behavior, delinguency, teen motivation and selfefficacy) predict response to the BEI. It is expected that poor response to treatment will be associated with high ADHD symptomatology, concurrent delinquency, risky sexual behavior, deviant peer affiliations, academic impairment, family conflict, lack of parent monitoring, poor self-efficacy and high motivation to use substances. Aim 3: We will also examine relative efficacy between the randomized second level interventions for BEI nonresponders (i.e., no treatment control, augmented psychosocial treatment (PT/ACBT) and combined medication and PT/ACBT) for non-responders to the BEI treatment. Adolescents who do not respond to the BEI and are randomized to the intervention arms of (PT/ACBT) or combined intervention (PT/ACBT+MED) will show differential improvements in primary and secondary outcomes (see Table 5). We hypothesize that relative to the no treatment control group, both groups will show improvements, with the largest effects for those who receive PT/ACBT+MED. Secondary analyses will be conducted for the one-year follow-up assessment for all groups. It is expected that therapeutic gains will extend through the follow-up period. Secondary analyses of treatment-related changes in the associated variables listed above will examine whether these changes mediate improvements in substance use. Analyses

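### BEI response is judged on 6-month use alone, so the rate pools teens whose use fell to normative with teens already normative at intake; report it by intake-use status

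*Combined protocol and SAP*

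**What the plan says.** In Hypotheses and Data Analysis, Aim 1 predicts that about 50% of adolescents will "show meaningful response to the BEI, as evidenced by no more than normative substance use assessed at 6-months following treatment". Research Design and Methods gives the mirror rule: "Non-response is defined as non-normative use of alcohol, marijuana, or other drugs in the past 90 days", and adds "Tobacco and caffeine products are excluded from consideration". Follow-up Assessment and Interventions again defines responders and non-responders by use after the BEI. None of the three places refers to use at intake.

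The Participants section sets eligibility: "Elevated risk is defined as the presence of at least risk factor from each of the following two categories of risk". In the substance-specific category, the teen's own use is one option of six: "Adolescent non-normative use of alcohol or other drugs indicated either by a positive urine drug screen or by adolescent self-report". The others include "Adolescent use of cigarettes or e-cigarettes indicated by self-report on the SUQ or the E-Cigarette Questionnaire" and "Perceived peer substance use indicated by adolescent report that at least one peer uses alcohol or other drugs", as well as elevated parental use, family history, and another child in the home who uses.

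On design, "no control condition is used in the current design at the first level of intervention".

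Under Analyses, Aim 1 is tested by a repeated-measures GLM of days and quantity of use from baseline to 6 months. A secondary analysis follows the percentage still at normative use at each randomisation point with Cox regression, for which no covariates are named. Aim 2 puts predictors into the same GLM and, optionally, into the Cox model.

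**The concern.** A teen can enrol because a friend drinks, or because of cigarettes alone, have no non-normative alcohol or drug use at intake, show none at 6 months, and be counted as having responded meaningfully to the BEI. Staying normative is a legitimate aim for at-risk youth, and the Interventions section describes the parent programme as serving such youth. But it is a different outcome from bringing non-normative use down, and the plan reports the two under one name.

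With no control at this stage, nothing else in the plan separates them. The Abstract expects lower response than in non-ADHD populations. That comparison depends on how many teens were already normative at intake, and the pooled rate hides this.

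The same mixture reaches two analyses. The Cox analysis puts both groups on one curve. In Aim 2, a predictor that does no more than mark intake use can appear to predict outcome.

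**Working it through.** **The plan's own figure.** 300 × (1 − 0.50) = 150, which matches the non-responder pool of at least 150 stated under Aim 3. The 50% is a planning expectation and cannot be derived from the documents.

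**Set-up.** Let p be the share non-normative at intake, i the share of intake-normative teens who become non-normative by 6 months, and q the share of intake non-normative teens who become normative. The documents give none of these, so every value below is assumed. The observed rate is

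R = (1 − p)(1 − i) + p·q, so q = [R − (1 − p)(1 − i)] / p.

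The share of responders already normative at intake is (1 − p)(1 − i) / R.

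Example with R = 0.50, p = 0.6, i = 0.10: q = (0.50 − 0.4 × 0.9)/0.6 = 0.233, and the already-normative share is 0.36/0.50 = 72%.

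**A second way to fill in i.** Low initiation is a strong assumption. At p = 0.5, i = q = 0.10 needs a latent pre-post correlation of about 0.95. The only correlation in the documents is 0.25, which the Power Analysis states for the medication interaction. I therefore also used a bivariate-normal model for use at the two times, with cut-points giving p non-normative at intake and 50% normative at 6 months. At p = 0.5 the probability of being normative at both times is 1/4 + arcsin(r)/(2π): 0.290 at r = 0.25 and 0.333 at r = 0.5. Dividing by 0.5 gives 58% and 67% staying normative, so q is 42% and 33%.

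At an observed 50%, each cell shows q, then the already-normative share of responders:

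| Assumption | p=.5 | p=.6 | p=.7 | p=.8 |
|---|---|---|---|---|
| i = 0 | 0%; 100% | 17%; 80% | 29%; 60% | 37.5%; 40% |
| i = 10% | 10%; 90% | 23%; 72% | 33%; 54% | 40%; 36% |
| r = .5 | 33%; 67% | 37%; 56% | 40%; 44% | 43%; 31% |
| r = .25 | 42%; 58% | 43%; 48% | 45%; 37% | 47%; 26% |

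At p = 1 the two readings coincide: q = 50% and no responder was already normative.

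**Effect on a responder-status model.** Assume a binary predictor present in 60% of intake non-normative teens and 40% of the others, unrelated to outcome within either group. At p = 0.5, i = q = 0.10:

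- non-response with the predictor: 0.6 × 0.9 + 0.4 × 0.1 = 0.58;
- non-response without it: 0.4 × 0.9 + 0.6 × 0.1 = 0.42;
- crude odds ratio: (0.58/0.42)/(0.42/0.58) = 1.91.

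Over p = .5 to .8 the crude odds ratio is 2.25 to 1.38 with no initiation, 1.91 to 1.30 with 10% initiation, 1.31 to 1.20 at r = .5 and 1.14 to 1.10 at r = .25. Within strata it is 1.0 by construction. The plan specifies no logistic model, so this is only an illustration; no hazard ratio was computed.

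**Effect on the Aim 2 GLM.** Under the same normal model with p = 0.5 and no treatment effect, intake groups differ in change by 2(1 − r) × 0.798: 1.20 SD at r = .25 and 0.80 SD at r = .5. At p = 0.5 the 60/40 predictor separates intake status by 0.6 − 0.4 = 0.2. It therefore shows a spurious difference in change of 0.2 × 1.20 = 0.24 SD or 0.2 × 0.80 = 0.16 SD. The Power Analysis uses an effect size of 0.25 for Aim 1. The artefact makes the predictor look linked to a larger fall in use, the opposite direction from the responder-status model.

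**The case against.** The strongest reply is that the powered Aim 1 analysis already uses baseline. It tests change in days and quantity of use, and the Interventions section names those same measures for evaluating treatment response. The 50% is not a tested threshold, and the Cox outcome is worded as maintaining normative use, not as response. All of this stands. A reader might infer that the Aim 1 test is invalid; the documents do not support that. The only qualification is that a teen with zero days at intake can only stay level or rise, so the mean change also averages over the two groups.

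Second, the intake mix may make the problem small. Potential Risks speaks of targeting substance users, and Importance of the Knowledge to be Gained speaks of emerging use. Both suggest a high p, where pooling matters less. But the eligibility rule does not guarantee it.

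Third, the large figures come from low initiation. That is fair: at the correlations tried, normalisation is 33% to 47% and the odds ratio 1.1 to 1.3. A reader might infer that most responders never had anything to reduce, but that holds only in some of the assumed scenarios.

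Fourth, the covariate list without intake use belongs to the repeated-measures GLM, where intake use should not be added. It does not show that intake status was deliberately left out of the Cox model, which is simply unspecified on this point.

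**Conclusion.** The point holds as a matter of definition: followed exactly, the plan labels an unchanged, already-normative teen as a responder, and the overall rate cannot be read as the share whose use fell to normative. Its size is not known. With an observed 50% and p from .5 to .8, the true normalisation rate among intake non-normative users runs from 0% to 47%, and the already-normative share of responders from 100% down to 26%. These figures rest on assumed p, initiation and correlation, and the effect vanishes as p approaches 1.

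What is affected is the interpretation of the stated response rate and the secondary Cox analysis. The Aim 2 GLM is not immune, because regression to the mean can give a predictor that tracks intake use a spurious predictor-by-time effect. The 0.16 to 0.24 SD figure rests on normality and an assumed 60/40 split. The Aim 1 test of change stands. Grade: minor to should-fix, a cheap improvement.

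**What to change.** - Report 6-month status in two rows: *response* (non-normative to normative) among teens non-normative at intake, and *maintained normative use* among the rest.
- Classify both times by the same past-90-day Substance Use Questionnaire rule. Do not use the own-use eligibility factor, which states no time window. Confirm that the Baseline Version listed in Table 5 yields that window.
- Present both rates as descriptive. Without a control, a BEI effect cannot be told apart from regression to the mean, spontaneous remission or initiation.
- Stratify the Cox model, and any model of responder status, by intake-use status.
- Do not add intake use or an intake-use-by-time term to the repeated-measures GLM: baseline use is already its first outcome, and conditioning on it creates the artefact shown above. State instead that Aim 2 predictor-by-time effects may reflect regression to the mean where the predictor tracks intake use.
- The Aim 3 randomisation trigger is unchanged.

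The cost is SAP wording, one extra table and a less precise response rate. With 15% dropout, 300 × 0.85 = 255 are analysed. The 95% half-width, 1.96 × √[R(1 − R)/n], for a 50% rate is 6.1 points at n=255 and about 8.7 at n=128 (p = .5). For a 90% maintenance rate at n=127 it is about 5.2 points. The questionnaire is already scheduled at both visits, so no new data are needed if the baseline window is confirmed.
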